APPENDIX 2. SIMPLE ENDOSCOPIC SCORE FOR CROHN'S DISEASE (SES-CD)

The simple endoscopy score (SES-CD) assesses the degree of inflammation. The SES-CD assesses the following 4 components: size of ulcers, ulcerated surface, affected surface, and presence of narrowings. Each of these components are scored on a scale of 0 to 3 as outlined below:

Table 9. Definitions of Simple Endoscopic Score for Crohn's Disease

Variable	SES-CD Values			
	0	1	2	3
Size of ulcers	None	Aphthous ulcers (< 0.5 cm)	Large ulcers (0.5 to 2 cm)	Very large ulcers (>2 cm)
Ulcerated surface	None	<10%	10-30%	>30%
Affected surface	Unaffected segment	<50%	50-75%	>75%
Presence of narrowings	None	Single, can be passed	Multiple, can be passed	Cannot be passed

In the SES-CD, each of these 4 components are assessed in the five segments of the ileum and colon: ileum, right, transverse, left (descending and sigmoid), and rectum. The SES-CD is the sum of the individual scores of each of the components across the five segments. Sub-scores for each segment will be derived and used to create SES-CD.

SES-CD sub-scores

- SES-CD rectum
- SES-CD left colon
- SES-CD transverse colon
- SES-CD right colon
- SES-CD ileum

APPENDIX 3. CDAI SCORE CALCULATIONS

The Crohn’s Disease Activity Index (CDAI) is a composite score that is used to measure the clinical activity of Crohn’s disease. The CDAI uses a questionnaire with responses scored numerically and weighted. Scores typically range from 0 to approximately 600, with higher scores indicating greater disease activity. The 8 components used to assess the CDAI, their weighting factors and calculation rules are noted in the table below. The number of stools, abdominal pain and general well-being are patient-reported outcomes which will be entered daily into an e-diary by patients. The Hematocrit component will be coming from the lab data and the other 4 components will be entered by the site at each visit.

Table 10. Score calculations, weights, and rules associated with CDAI, its components, and associated endpoints

Item	Weight	Algorithm

Number of liquid or soft stools (CDAI sub-score)
	
2
	
 • Use the most recent 7 days prior to the visit date in Rave EDC database; excluding the day prior and the day of the endoscopy, as applicable. • Define: SF = average daily stool score = average of the number of liquid/soft stools for the available days in the 7-day window • If there are less than 3 days with non-missing values, then set SF to missing • If there are 7 days of data available, then the CDAI sub-score is equal to the sum of the 7 days*2; otherwise, the CDAI sub-score is equal to the average daily stool score*7*2; as a formula, this is written as $\text{CDAI sub-score} = \text{SF} * 7 * 2$ in both cases

Abdominal pain (CDAI sub-score)
	
5
	
 • Use the most recent 7 days prior to the visit date in Rave EDC database; excluding the day prior and the day of the endoscopy, as applicable. • Define: AP = average daily abdominal pain score = average of the abdominal pain level for the available days in the 7-day window • If there are less than 3 days with non-missing values, then set AP to missing

		
 If there are 7 days of data available, then the CDAI sub-score is equal to the sum of the 7 days*5; otherwise, the CDAI sub-score is equal to the average daily abdominal pain score*7*5; as a formula, this is written as CDAI sub-score = AP*7*5 in both cases
General well-being (CDAI sub-score)	7	
 Use the most recent 7 days prior to the visit date in Rave EDC database; excluding the day prior and the day of the endoscopy, as applicable. Define: GW = average daily general well-being score = average of the general well-being level for the available days in the 7-day window If there are less than 3 days with non-missing values, then set GW to missing If there are 7 days of data available, then the CDAI sub-score is equal to the sum of the 7days*7; otherwise, the CDAI sub-score is equal to the average daily general well-being score *7*7; as a formula, this is written as CDAI sub-score = GW*7*7 in both cases
Presence of complications* (CDAI sub-score)	20	
 Sum=Total of the number of checked complications CDAI sub-score = Sum * 20.
Taking diarrhea meds* (CDAI sub-score)	30	
 Variable: Yes=1; No=0 CDAI sub-score = Variable * 30
Abdominal mass* (CDAI sub-score)	10	
 Variable: No=0; Questionable=2; Definite=5 CDAI sub-score = Variable * 10
Hematocrit (CDAI sub-score)	6	
 Hematocrit (HCT) is obtained from the Hematology lab panel and can be found in the SDTM LB domain

		
 • If HCT is missing, use the last non-missing value immediately preceding the time point; if the immediately preceding time point value is missing too, then set to missing • Men: $\text{CDAI sub-score} = (47 - \text{HCT}) * 6$ • Women: $\text{CDAI sub-score} = (42 - \text{HCT}) * 6$ • If $\text{CDAI sub-score} < 0$, it will be recorded as 0
Percentage deviation from standard weight (CDAI sub-score)	1	
 • The standard weight table was provided by Celgene to ERT for integration into the SitePro tablet algorithms (height in cm and weight in kg); ERT created four conversion tables which will be used in statistical analysis so that the %deviation from standard weight is automatically calculated by the ERT system, which allows ERT to calculate estimated CDAI scores embedded in their monthly SitePro.sas7bdat datasets. It is noted that these are CDAI estimates only and not for use in production TFLs. • If weight is missing, use the last non-missing %deviation from standard weight value immediately preceding the time point; if the immediately preceding time point value is missing too, then set %deviation from standard weight to missing • $\text{CDAI sub-score} = \text{%deviation from standard weight}$; it should be ≥ -10 (i.e., -10, -9; if calculated value is < -10, it will be recorded as -10) in all cases
CDAI (CDAI endpoint)	n/a	
 • $\text{CDAI endpoint} = \text{sum of the above 8 CDAI sub-scores}$. If any of the 8 sub-scores are missing, then the CDAI endpoint score is missing.
PRO2 (CDAI associated endpoint)	n/a	
 • $\text{PRO2} = \text{weighted sum of SF and AP} = \text{SF} * 7 * 2 + \text{AP} * 7 * 5$. If either SF or AP are missing, then PRO2 is missing.
SF/AP (CDAI associated endpoint – included only for reference)	n/a	
 • $\text{SF/AP} = \text{unweighted sum of SF and AP} = \text{SF} + \text{AP}$. If either SF or AP are missing, then SF+AP is missing.

*: The visit date that is used to calculate the relative study day will be taken from Rave, instead of the system generated date in Sitepro.

In computing number of liquid or soft stools, abdominal pain, and general well-being, the date corresponding to Day 1 will be used as the baseline date. Dates for post-baseline visits will be obtained from the dates when CDAI components of extra-intestinal manifestations, opiate for diarrhea, abdominal mass findings, and weight were assessed at the site.

For computing the CDAI total, following steps are followed for combining the individual components:

- For Baseline visit, the components excluding hematocrit will be merged by patient, visit, and analysis date. For post-Baseline visits, components excluding hematocrit will be merged by patient, visit, analysis visit, analysis date, and imputation. Then the seven components are summed.
- Merge with hematocrit values by patient for the analysis visit at Baseline, and patient, visit, analysis visit, analysis date, and imputation, for post-Baseline visits.
- Add hematocrit value to the sum of the seven components from previous steps.

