- ⁱ Week 12 colonoscopy should be performed either on day of visit or no more than 7 days prior to the visit date.
- ^j Colonoscopy does not need to be performed at the Early Term visit if one was completed within 8 weeks of the Early Term visit.
- ^k Enterocutaneous and perianal fistula drainage assessment will only be performed on patients with fistulas at baseline.
- ^l Blood samples for PK evaluation are to be taken up to 15-30 minutes prior to investigational drug administration (pre-dose) and just prior to discharge from the clinic (6-8 hours post-dose) on Day 1. Blood samples at subsequent visits will be trough level, taken just prior to investigational drug administration. The actual time of investigational drug administration for all visits with PK evaluation will be recorded. The blood sample at the 30-day and 90-day Safety Follow-Up Visit can be collected at any point during the visit. An additional PK sample will be obtained for patients with any AE resulting in discontinuation or SAE.
- ^m Week 12 flow cytometry analysis will only be performed for patients with a baseline sample (Day 1).
- ⁿ Prior to first dose of investigational drug, a 12-lead ECG will be performed. After the dose, patients will have hourly vital signs recorded at 1, 2, 3, 4, 5, and 6 hours post-dose. A second 12-lead ECG will be performed at the end of the observation period.

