| | Trial Procedures | Extension Period | | | | | | | | | | | | | | Early Term | Safety Follow-up | |
|--|------------------------------|-------------------|-----------------|-----------------|-----------------|-----------------|-----------------|-----------------|-----------------|-----------------|------------|------------|------------|-------------|------------------|-------------------|-----------------------|-------------------------------------|
| | | Treatment | | | | | | | | | | | | | | | | |
| | | E1 ^{a,b} | E2 ^b | E3 ^b | E4 ^b | E5 ^b | E6 ^b | E7 ^b | E8 ^b | E9 ^b | E10 | E11 | E12 | E13 | E14 ^b | | | |
| | | W12 | W 24 | W 36 | W 48 | W 52 | W 64 | W 76 | W 88 | W 100 | W 112 | W 124 | W 136 | W 148 | W 160 | | | |
| | | Day 84 ±3 | Day 168 ±7 | Day 252 ±7 | Day 336 ±3 | Day 364 ±3 | Day 448 ±7 | Day 532 ±7 | Day 616 ±7 | Day 700 ±7 | Day 784 ±7 | Day 868 ±7 | Day 952 ±7 | Day 1036 ±7 | Day 1120 ±7 | Day of Early Term | Last dose +30 ±3 days | Last dose +90 ±10 days ^j |
| | Optical coherence tomography | | | | | X | | | | | X | | | | X | X | | |

- ^a The duration of Visit E1 will be approximately 3 hours.
- ^b Trial visits should be scheduled in the morning, when possible. At trial Visits Week 24, 52 and at Week 160, patients should be instructed to withhold the dose until the trial visit and the dose should be administered during the visit.
- ^c At Week 52, a colonoscopy should be performed either on the day of visit or no more than 7 days prior to the visit date.
- ^d Colonoscopy, biopsy, and SES-CD score do not need to be performed at the Early Term visit if the Early Term Visit occurs within 8 weeks of the Week 12 colonoscopy or after the Week 52 colonoscopy assessment.
- ^e Enterocutaneous and perianal fistula drainage assessment will only be performed on patients with fistulas at baseline.
- ^f Blood samples at each visit will be trough level, taken just prior to investigational drug administration. The actual time of investigational drug administration for all visits with PK evaluation will be recorded. The blood sample at the Follow-up visit can be collected at any point during the visit. An additional PK sample will be obtained for patients with any AE resulting in discontinuation or SAE.

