11.1.3. Crohn's Disease Activity Index

The Crohn's Disease Activity Index (CDAI) is a composite score that is used to measure the clinical activity of Crohn's disease. The CDAI uses a questionnaire with responses scored numerically and weighted. Scores range from 0 to approximately 600, with higher scores indicating greater disease activity. The 8 components used to assess the CDAI and their weighting factors are noted in [Table 6](#). The definitions of mild, moderate, and severe Crohn's disease are provided in [Table 7](#).

Patient-reported outcomes (stool frequency and abdominal pain components of the CDAI Score and general well-being), and the other CDAI components will be collected in an electronic diary. Patients will complete the stool frequency, abdominal pain and general well-being components of the CDAI from the patient’s first screening visit and will continue throughout the trial.

Patients will be instructed on the use and completion of questions on the electronic diary.

The diary entries will be reviewed by site personnel during screening (prior to dosing, if applicable) and during all trial visits. The stool frequency and abdominal pain diary entries preceding each trial visit will be used to calculate the CDAI score and will be calculated using the stool frequency and the abdominal pain data from the most recent 7 day period, or at least 3 days within that 7 day period, prior to the visit, excluding the following:

- One day prior to the start of a procedure or preparation for a procedure that would affect stool frequency
- The day(s) of a procedure or preparation for a procedure that would affect stool frequency

Because the colonoscopy preparations can interfere with the assessment of other clinical parameters, diary entries used to calculate the CDAI score will not correspond to day(s) of bowel preparation or endoscopy.

Table 6: CDAI Assessment

| Clinical or Laboratory Variable | Weighting Factor, × |
|---|----------------------------|
| Number of liquid or soft stools each day for 7 days | 2 |
| Abdominal pain (graded from 0-3 on severity) each day for 7 days | 5 |
| General well-being, assessed from 0 (well) to 4 (terrible) daily for 7 days | 7 |
| Presence of complications* | 20 |
| Taking diphenoxylate/atropine, loperamide, or opiates for diarrhea | 30 |
| Presence of an abdominal mass (0 as none, 2 as questionable, 5 as definite) | 10 |
| Hematocrit 47-HCT in men and 42-HCT in women | 6 |

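### SAP Table 10 removes fewer diary days around colonoscopy than Protocol 11.1.3, so stool, pain, CDAI and PRO2 scores at Weeks 12 and 52 can differ from those the protocol defines

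*SAP*

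**What the plan says.** Protocol Section 11.1.3 names two kinds of diary day that may not be used for stool frequency and abdominal pain: "One day prior to the start of a procedure or preparation for a procedure that would affect stool frequency" and "The day(s) of a procedure or preparation for a procedure that would affect stool frequency". It closes by saying, of the CDAI as a whole, that "diary entries used to calculate the CDAI score will not correspond to day(s) of bowel preparation or endoscopy". At least three days of the seven must remain.

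SAP Appendix 3, Table 10 gives the programming rule: "Use the most recent 7 days prior to the visit date in Rave EDC database", then "excluding the day prior and the day of the endoscopy, as applicable". The same words appear for stools, abdominal pain and general well-being. The minimum is kept: "If there are less than 3 days with non-missing values, then set SF to missing", with matching lines for the other two items. Neither preparation days nor procedures other than endoscopy are mentioned.

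Colonoscopy falls in or beside this window. Protocol Table 2 says: "Week 12 colonoscopy should be performed either on day of visit or no more than 7 days prior to the visit date". Table 3 says: "At Week 52, a colonoscopy should be performed either on the day of visit or no more than 7 days prior". The screening colonoscopy must fall within 14 days of Day 1 (Table 2, footnote h), and SAP Appendix 3 anchors the baseline diary window on Day 1.

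**The concern.** The SAP rule is narrower than the protocol rule, and programmers will follow the SAP. The averages concerned feed CDAI change, CDAI response and remission, PRO2 response, SF&AP remission, and the separate stool and pain changes (SAP Section 4.2.2). Weeks 12 and 52 are the only visits at which proportions receive confidence intervals (SAP Section 9.4), and they are the visits with a colonoscopy. If a bowel-preparation day stays in the window, laxative stools count as disease activity. SAP Section 12 is where departures from the protocol are recorded, and its readable text does not record this one.

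**Working it through.** **Inputs.** Let V be the visit and E the colonoscopy day.
- Diary window: V−7 to V−1 (SAP Table 10).
- Permitted E at Weeks 12 and 52: V−7 to V, which is 8 days (Protocol Tables 2 and 3).
- SAP removes E−1 and E.
- Protocol, for stools and pain, removes E, all L preparation days (E−L to E−1), and the day before preparation, E−L−1.
- L is not given in either document. I assume 1, 2 or 3 days ending on E−1. If preparation took place wholly on the procedure day, the two rules would coincide.

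**Days kept (stools and pain).**

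| L | E | SAP keeps | Protocol keeps | Preparation days kept by SAP |
|---|---|---|---|---|
| 1 | V | 6 | 5 | 0 |
| 1 | V−1 to V−5 | 5 | 4 | 0 |
| 2 | V | 6 | 4 | 1 |
| 2 | V−1 to V−4 | 5 | 3 | 1 |
| 2 | V−5 | 5 | 4 | 1 |
| 3 | V | 6 | 3 | 2 |
| 3 | V−1 to V−3 | 5 | 2 (score missing) | 2 |
| 3 | V−4 | 5 | 3 | 2 |
| 3 | V−5 | 5 | 4 | 1 |
| 1, 2 or 3 | V−6 | 5 | 5 | 0 |
| 1, 2 or 3 | V−7 | 6 | 6 | 0 |

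The day on which the rules first part is E−2. It lies in the window when E is V−5 to V, which is 6 of the 8 permitted days. For L = 1, E−2 is an ordinary day. For L = 2 or 3, it is a preparation day.

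At baseline, counting E from 14 days to 1 day before Day 1, E−2 lies in the window for 5 of 14 positions (Day 1 minus 5 to Day 1 minus 1).

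**Effect of one retained preparation day.** With x extra stools on that day and k days kept, stool frequency rises by x/k. CDAI and PRO2 each rise by 14·x/k, because both weight stool frequency by 7 × 2 = 14. The values of x are assumptions.

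| x | k | Rise in stool frequency | Rise in CDAI or PRO2 |
|---|---|---|---|
| 5 | 6 | 5/6 = 0.83 | 11.7 |
| 5 | 5 | 5/5 = 1.0 | 14.0 |
| 10 | 6 | 10/6 = 1.67 | 23.3 |
| 10 | 5 | 10/5 = 2.0 | 28.0 |

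For L = 1 the preparation effect is zero.

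**Example.** A patient averages 2.5 stools a day, with colonoscopy on the visit day (k = 6) and 5 extra stools on one retained preparation day. Under the SAP the average is 2.5 + 5/6 = 3.33, which fails the stool criterion of at most 3 for SF&AP remission. Under the protocol it is 2.5, which meets it.

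**Direction.** At Week 12 or 52 a retained preparation day raises the score and works against response and remission. At baseline it enlarges the apparent fall in CDAI and PRO2. The remission definitions use absolute thresholds and do not depend on baseline.

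**The case against.** The strongest objection is that the harm is conditional. If preparation is confined to the day before colonoscopy, the SAP removes every preparation and procedure day and satisfies the protocol's closing sentence. What remains is one ordinary diary day kept. This stands: a reader might infer that laxative stools necessarily enter the scores, and the documents do not support that, because they give no preparation length.

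A reader might also infer that the rule flatters the drug. That could happen only through baseline. At Weeks 12 and 52 the bias runs the other way, and if it occurs at both times the changes partly cancel.

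Nor can one say that SAP Section 12 omits the change altogether. Some of its bullets are redacted, so only the readable text can be relied on.

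The gap on procedures other than endoscopy carries little weight. Colonoscopy is the only scheduled procedure that needs bowel preparation. Patients who have a CD-related resection or stricture dilation are in any case treatment failures, and so non-responders in the proportion endpoints (SAP Sections 5.5.4 and 9.1).

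Finally, the protocol's bulleted exclusions govern stool frequency and pain. General well-being is reached only by the closing sentence, which does not exclude the day before preparation.

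None of this removes the conflict. The two rules select different days even with one-day preparation.

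**Conclusion.** The two documents define different diary windows, and the difference should be reconciled. For 6 of the 8 permitted colonoscopy days at Weeks 12 and 52, the SAP keeps at least one day the protocol excludes, provided preparation begins no later than the day before colonoscopy. Whether that day distorts the score depends on preparation length. With one-day preparation there is no laxative effect. With longer preparation, one retained day adds about 0.8 to 2.0 to stool frequency and about 12 to 28 points to CDAI or PRO2, assuming 5 to 10 extra stools and 5 or 6 days kept. This is well short of the 100-point CDAI response rule but enough to move a patient across the stool threshold for remission. The stakes are modest: the primary endpoint, change in SES-CD, does not use the diary, and no hypothesis is tested.

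**What to change.** In SAP Table 10:
- For stool frequency and abdominal pain, exclude every day from the day before preparation starts through the procedure day, for any procedure that alters stool counts.
- For general well-being, exclude at least all preparation and procedure days.
- Keep the 3-day minimum.
- State where preparation dates come from. The readable schedules have no item for them.

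If the narrower rule is intended, declare it in Section 12 with a reason.

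The cost is more than wording. Across most permitted colonoscopy days one usable diary day is lost, or two with 2-day preparation (6 against 4 when colonoscopy is on the visit day). With 3-day preparation and colonoscopy at V−1 to V−3, only two days remain. Stool frequency, pain, CDAI and PRO2 are then missing, and the patient counts as a non-responder under NRI and drops out of the observed-case summaries. The protocol already accepts this consequence through its own 3-day minimum.

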APPENDIX 4. GEBOES HISTOLOGY ACTIVITY INDEX AND ROBARTS HISTOPATHOLOGY INDEX

The following tables give details of the scoring for the Global Histologic Disease Activity Score (GHAS)^{3,4} and a newly developed scoring system entitled the Robarts Histopathology Index (RHI)⁵. Higher numbers correspond to more inflammation and mucosal damage. For each CD segment, the GHAS score can be treated as a continuous measure on a 16 point scale. For each CD segment, the RHI score can be treated as a continuous measure on a 33 point scale. Scoring for both indices will be performed for each segment (i.e., ileum, right, transverse, left (descending and sigmoid), and rectum) that is visualized and for which biopsy samples are available. Similar to the SES-CD, sub-scores for each segment will be derived.

The eight components used to assess the per-CD segment GHAS score are noted in the table below. The maximum per-CD segment total score is 16.

Table 11. GHAS Grading System

GHAS Descriptors and Levels	
Epithelial damage	0: Normal 1: Focal Pathology 2: Extensive Pathology
Architectural changes	0: Normal 1: Moderately disturbed (<50%) 2: Severely disturbed (>50%)
Infiltration of mononuclear cells in the lamina propria	0: Normal 1: Moderately increase 2: Severe increase
Infiltration of polypmorphonuclear cells in the lamina propria	0: Normal 1: Moderately increase 2: Severe increase
Polypmorphonuclear cells in epithelium	0: Normal 1: In surface epithelium 2: Cryptitis 3: Crypt abscess
Presence of erosion and/or ulcers	0: No 1: Yes
Presence of granuloma	0: No 1: Yes
Number of biopsy specimens affected	0: None (0 of 6) 1: ≤3% (1 or 2 of 6) 2: 33-66% (3 or 4 of 6) 3: >66% (5 or 6 of 6)

1

[REDACTED]

Exploratory GHAS Histologic Remission (no active inflammation in a measured segment) is defined in the following table, where the max overall GHAS score in a given segment must be less than or equal to 8, and each segment meets this standard:

Table 12. Per-CD Segment GHAS Scores Allowed for Histologic Remission

Epithelial damage	0
Architectural changes	0-2
Infiltration of mononuclear cells in the lamina propria	0-2
Infiltration of polymorphonuclear cells in the lamina propria	0
Polymorphonuclear cells in epithelium	0
Presence of erosion and/or ulcers	0
Presence of granuloma	0-1
Number of biopsy specimens affected	0-3

The four components used to assess the per-CD segment RHI score are noted in the table below. The maximum per-CD segment total score is 33.

Table 13. Roberts Histopathology Index (RHI) Grading System

Subcomponent Descriptors	Scores	Weighting factor
Chronic inflammatory infiltrate	0=No increase 1=Mild but unequivocal increase 2=Moderate increase 3=Marked increase	1
Lamina propria neutrophils	0= None 1= Mild but unequivocal increase 2=Moderate increase 3=Marked increase	2
Neutrophils in epithelium	0=None 1 = <5% crypts involved 2= <50% crypts involved 3= >50% crypts involved	3
Erosion or ulceration	0=No erosion, ulceration or granulation tissue 1=Recovering epithelium + adjacent inflammation OR probable erosion-focally stripped 2=Unequivocal erosion 3=Ulcer or granulation tissue	5

An exploratory RHI Histologic Remission (no active inflammation in a measured segment) is defined in the following table. The maximum per-CD segment RHI score allowable for a segment to qualify for RHI Histologic Remission is 3. A patient not meeting at least one of the criteria 2, 3, or 4, below in a segment is defined as a non-RHI remitter for that segment. Note that criteria 1 is always met.

Table 14. Per-CD Segment RHI Scores Allowed for Histologic Remission

Subcomponent Descriptors	Scores	Weighting factor
Chronic inflammatory infiltrate	0-3	1
Lamina propria neutrophils	0	2
Neutrophils in epithelium	0	3
Erosion or ulceration	0	5

Global RHI Score

Global RHI Score is a weighted sum of the worst, i.e., the highest, of each of the four disease component scores across the four colonic segments, rectum, left colon, transverse colon, and right colon. Same weighting factors used in computing the RHI Score is used.

Global RHI Score = 1x highest Chronic inflammatory infiltrate score + 2x highest Lamina propria neutrophils score + 3x highest Neutrophils in epithelium score + 5x highest Erosion or ulceration score.

